11.3 EFFICACY ANALYSES

Not applicable.

11.4 PK ANALYSES

The primary analysis set for summaries of PK data will be the PK Set. If the PK Set and the Safety Set are not equivalent, then all PK summaries described below will also be produced for the Safety Set.

11.4.1 Plasma Concentration Data

Plasma PK samples will be collected for measurement of cytosine at the following time points:

- Day 1, first dose: Pre-first dose, 0.5h, 0.75h, 1h, 1.25h, 1.5h, 2h;
- Day 1, last dose: Pre-last dose, 0.5h, 1h, 1.5h, 2h, 2.5h, 3h, 3.5h, 4h, 5h;
- Days 2 and 3: Pre-last dose, 0.5h, 1h, 1.5h, 2h, 2.5h, 3h, 3.5h, 4h, 5h;
- Days 4, 13, 17, 21: Pre-first dose;
- Days 12, 16, 20, 24: Pre-last dose, 1h, 1.5h, 2h, 2.5h, 3h, 3.5h, 4h;
- Day 25: Pre-dose, 0.5h, 0.75h, 1h, 1.25h, 1.5h, 1.75h, 2h, 2.25h, 2.5h, 2.75h, 3h, 3.25h, 3.5h, 3.75h, 4h, 5h, 6h, 8h, 10h, 12h, 24h.

Cytosine concentrations in plasma will be listed and summarised by dose group and age group using the descriptive statistics N, n, arithmetic mean, arithmetic standard deviation (SD), coefficient of variation (CV%), minimum, median and maximum.

The individual subject plasma cytosine concentration profiles over time will be presented graphically using actual blood sampling times on a linear and semi-logarithmic scale. Arithmetic mean plasma cytosine concentration profiles over time will be presented on linear and semi-logarithmic scales with profiles presented for each study day as appropriate and a separate plot for each dose group and age group.

For inclusion within the summary tables and linear scale plots, concentrations below the limit of quantification (BLQ) will be assigned a value of zero. For inclusion within the semi-logarithmic scale plots, concentrations below the limit of quantification (BLQ) will be set to missing. Concentrations above the upper limit of quantification (ULOQ) will be obtained via dilution into the calibration range and are valid results.

Plasma concentration data listings and individual plots will be presented using the Safety Set. Plasma concentration data summaries and mean plots will be presented using the PK Set and the Safety Set. All plasma concentration data included in listings and summaries will be presented to three significant figures.

11.4.2 Urine Concentration Data

Urine PK samples will be collected for measurement of cytosine on Day 1 and Day 25 at the following time intervals: Pre-dose (taken upon waking), 0-24h post-dose.

Cytisine concentrations in urine will be listed and summarised for each dose group and age group using the descriptive statistics N, n, arithmetic mean, arithmetic standard deviation (SD), coefficient of variation (CV%), minimum, median and maximum.

Urine concentration data listings will be presented using the Safety Set. Urine concentration data summaries will be presented using the PK Set and the Safety Set.

11.4.3 Derived PK Parameters

The derived pharmacokinetic parameters of cytisine in plasma (listed in section 4) will be determined using WinNonlin Phoenix 6.4 from the individual concentration versus time data using standard non-compartmental methods. The derived urine pharmacokinetic parameters, Ae and Ae% (individual and cumulative), will be determined from the individual concentration versus time data using SAS version 9.3.

For the calculation of derived pharmacokinetic parameters, concentrations below the limit of quantification (BLQ) will be assigned a value of zero. In case of a deviation from the theoretical time, the actual time of blood sample will be used in the calculation of the derived pharmacokinetic parameters.

The terminal elimination rate constant (λ_z) will be determined by plotting the concentration data versus time on a semi-logarithmic scale. The parameter will be estimated by linear least square regression analysis, using the last three (or more) non-zero concentrations. The upper and the lower time points, as well as the number of time points, used for λ_z estimation will be reported.

AUC_{0-t} will be calculated using the linear-up/log-down trapezoidal method.

The derived urine PK parameter Ae will be calculated from as: urine volume * urine cytisine concentration. Ae% will be derived as: $100 * Ae / Dose$.

Values of λ_z , $AUC_{0-\infty}$, %AUC and $t_{1/2}$ will not be reported for cases where λ_z cannot be reliably determined.

C_{max} (and T_{max}) will be calculated after the first dose and the last dose on Day 1, after the last dose on days 2, 3, 12, 16, 20, 24 and after the morning dose on Day 25. C_{max} and T_{max} values will be calculated as follows:

- On Day 1, C_{max} after the first daily dose will be estimated from venous blood samples collected 0.5h, 0.75h, 1h, 1.25h, 1.5h, and 2h after the first dose.
- On Day 1, Day 2, and Day 3 estimates of C_{max} after the last daily dose will be made from venous blood samples collected 0.5 h, 1h, 1.5h, 2h, 2.5h, 3h, 3.5h, 4h, and 5h following the last dose.
- On Day 12, 16, 20, and 24, C_{max} estimates will be made from venous blood samples collected 1h, 1.5h, 2h, 2.5h, 3h, 3.5h, and 4h after the last daily dose.
- On Day 25 C_{max} will be estimated from venous blood samples collected 0.5h, 0.75h, 1h, 1.25h, 1.5h, 1.75h, 2h, 2.25h, 2.5h, 2.75h, 3h, 3.25h, 3.5h, 3.75h, 4h, 5h, 6h, 8h, 10h, 12h, and 24h post-dose.

C_{min} will be derived from the pre-first dose plasma values on days 4, 13, 17, 21 and 25.

The $t_{1/2}$, λ_z , AUC_{0-t} , AUC_{0-inf} and %AUC_{extrap} values will be determined after the administration of the final dose of cytisine on Day 25. On Day 25 $t_{1/2}$ and AUC will be determined after the administration

of the final dose of cytosine from venous blood samples collected 0.5h, 0.75h, 1h, 1.25h, 1.5h, 1.75h, 2h, 2.25h, 2.5h, 2.75h, 3h, 3.25h, 3.5h, 3.75h, 4h, 5h, 6h, 8h, 10h, 12h, and 24h post-dose.

The derived urine parameters Ae and Ae% will be calculated from 0-24h on Day 1 and Day 25.

Derived pharmacokinetic parameters will be listed and summarised for each dose group and age group. The descriptive statistics presented will be N, n, arithmetic mean, arithmetic standard deviation (SD), coefficient of variation (CV%), minimum, median, maximum and geometric mean (with the exception of T_{max}).

PK parameter data listings will be presented using the Safety Set. PK data summaries will be presented using the PK Set and the Safety Set. All PK parameter data included in listings and summaries will be presented to three significant figures with the exception of the CV% which will be presented to one decimal place.

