**Figure 1: Marketed Dosing (1.5 mg tablet) and Timing schedule for [REDACTED]**

## 2.3. Recent Cytisine Pharmacokinetic Studies

### 2.3.1. Study CYT-BIO-02-07 in Healthy Subjects

The Phase 1 CYT-BIO-02-07 study enrolled 36 healthy male subjects who received a single oral dose of 1.5 mg cytisine under fasting conditions. Blood sampling and quantitative urine collection for the determination of cytisine in plasma and urine were performed at regular intervals during the treatment period. Physical examinations were performed by the Principal Investigator or designee at the pre-study screening, after admission to the clinical center, and during the evening before drug administration to the post-study examination just prior to discharge from the clinic. Vital signs (blood pressure, heart rate, and temperature) were also performed after admission to the clinical center, during the evening before drug administration, and within 30 min before drug administration (pre-dose), and 2, 4, 12, and 24 h after drug administration during the Treatment Period.

Blood sampling for determination of cytisine concentrations was carried out in the treatment period within 30 min before (pre-dose) and at 5, 10, 20, 30, 40, and 50 min and continued at 1.0; 1.25; 1.50; 1.75; 2.0; 2.25; 2.50; 3.0; 4.0; 5.0; 6.0; 8.0, and 10.0 h after administration of 1.5 mg cytisine (one [REDACTED] tablet). Urine was collected before (baseline) and quantitatively during the intervals 0-3, 3-6, 6-9, 9-12, and 12-24 h after administration of study drug. At the end of each collection interval, individual urine portions were pooled and aliquots were withdrawn from each urine pool. Creatinine concentrations were measured for each urine pool. Plasma and urine levels of cytisine were determined using validated LC-MS/MS analytical methods. Pharmacokinetic parameters of cytisine in plasma that were estimated included  $AUC_{last}$ ,  $AUC_{inf}$ ,  $C_{max}$ ,  $T_{max}$ , and  $T_{1/2}$ .

Results showed that no measurable plasma levels of cytisine were observed 5 min after drug administration. After 10 min, a level exceeding the limit of quantitation (LOQ) was noted in 5 of 36 (14%) subjects; after 20 min, a level exceeding the LOQ was noted in 29 of 36 (81%)

subjects. At 10 h after drug administration, the cytisine plasma levels exceeded LOQ in all subjects. Mean values and other calculated PK parameters are presented in [Table 1](#) (extracted from the Study CYT-BIO-02-07 report).

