11.4.3.1 Statistical Analysis of PK Parameters

Dosing Schedule Comparison

The dosing schedule comparison analysis will be performed separately within each of the dose groups.

In order to perform comparisons between schedule changes within each dose group, following logarithmic transformation, C_{max} values (post-last dose on days 3, 12, 16, 20, 24 and 25), and C_{min} values (pre-first dose on days 4, 13, 17, 21 and 25) will be subjected to an analysis of variance (ANOVA) including a fixed effect for study day and a random effect of subject. Point estimates and 90% confidence intervals (CI) will be constructed for the contrasts between consecutive study days using the residual mean square error obtained from the ANOVA. The point and interval estimates will be back-transformed to give estimates of the ratios of the geometric least squares means (LSmean) and corresponding 90% CI. In addition, estimated geometric means will be presented. The analysis will be performed by age group (18-65 yrs, >65 yrs, all ages).

Dose Group Comparison

The dose group comparison will be a between-group analysis.

Following logarithmic transformation, C_{max} , AUC_{0-t} and AUC_{0-inf} values on Day 25 will be subjected to an analysis of variance (ANOVA) including a fixed effect for dose group. Point estimates and 90% confidence intervals (CI) will be constructed for the contrast between the 1.5 mg and 3.0 mg dose groups using the residual mean square error obtained from the ANOVA. The point and interval estimates will be back-transformed to give estimates of the ratios of the geometric least squares means (LSmean) and corresponding 90% CI. In addition, estimated geometric means will be presented. The analysis will be performed by age group (18-65 yrs, >65 yrs, all ages).

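### The SAP sets BLQ concentrations to zero and then log-transforms Cmin, so the Day 25/Day 21 Cmin ratio may be biased upward if Day 25 troughs fall below the LLOQ

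*SAP*

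**What the plan says.** SAP 11.4.3 fixes the handling of low concentrations for every derived parameter: "For the calculation of derived pharmacokinetic parameters, concentrations below the limit of quantification (BLQ) will be assigned a value of zero". In the same section Cmin "will be derived from the pre-first dose plasma values on days 4, 13, 17, 21 and 25", so each value is a single sample. The section also lists the geometric mean among the summary statistics for all derived parameters except Tmax.

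SAP 11.4.3.1 log-transforms Cmin and fits an ANOVA "including a fixed effect for study day and a random effect of subject", and "90% confidence intervals (CI) will be constructed for the contrasts between consecutive study days". Day 25 against Day 21 is one of these contrasts. Protocol 15.7 plans the same comparison on log-transformed data.

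Other sections deal with zeros only in other settings:
- SAP 11.4.1: "For inclusion within the semi-logarithmic scale plots, concentrations below the limit of quantification (BLQ) will be set to missing". This covers plots only.
- SAP 11.4.3 restricts the terminal-slope regression to non-zero concentrations.
- SAP 10.1 repeats the replacement by zero. It also allows alternative methods if assumptions fail, without naming one.
- SAP 10.3 covers missing samples, not BLQ results.

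Protocol 12.3 defers the LLOQ to a separate bioanalytical plan.

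**The concern.** Followed literally, the rules make a BLQ trough a Cmin of zero, which can enter neither the geometric mean nor the log-scale ANOVA. Nothing says what happens next. Unless someone intervenes, software returns a missing value and the record is lost.

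That loss is informative, because the records removed are the lowest ones. They would concentrate where troughs are lowest: Day 25, after the twice-daily phase, in the 1.5 mg group. Removing them raises the apparent Day 25 Cmin and understates the fall from Day 21.

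Cmin is listed among the primary variables in SAP 4.1, and the schedule contrasts are planned in both documents. They are repeated by age group, with about six elderly subjects per dose group. SAP 9.3 locks and reports the non-elderly data first, so a rule left open could end up being chosen after those troughs have been seen.

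**Working it through.** The plan states no LLOQ, expected Cmin ratio or power, so there is no figure of its own to reproduce. The check predicts the troughs from Protocol Table 1 and asks what dropping the BLQ values does to the ratio.

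**Inputs.** From Table 1 (single 1.5 mg dose): geometric mean Clast, sampled at 10 h, 2.10 ng/mL (CV 36%); terminal rate constant λz 0.1726/h (CV 19%). These agree with the rest of the table: ln 2/0.1726 = 4.02 h (table: 4.02) and 2.10/0.1726 = 12.17 (table AUCres: 12.19). The schedule is Protocol Figure 4. A 09:00 first dose (Protocol 8.8, stated for Day 1) is assumed on all days.

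**Typical troughs, 1.5 mg group.** A dose given t hours earlier contributes 2.10 × exp(−0.1726 × (t − 10)). Earlier days multiply the sum by 1/(1 − exp(−0.1726 × 24)) = 1.016.
- Day 25 (doses 18 and 24 h before): 0.528 + 0.187 = 0.715; × 1.016 = 0.73 ng/mL.
- Day 21 (doses 15, 19.5 and 24 h before, taking 4.5 h for the 4-5 h interval): 0.886 + 0.407 + 0.187 = 1.480; × 1.016 = 1.50 ng/mL.
- Ratio: 0.73/1.50, about 0.48.

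Under dose proportionality the 3.0 mg troughs are twice as high, so an LLOQ of 0.5 there acts like 0.25 in the 1.5 mg group.

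**Spread between subjects.** AUCres = Clast/λz, so the log-scale covariance of Clast and λz is (0.1219 + 0.0355 − 0.2476)/2 = −0.0451, a correlation of −0.69. The three variances are ln(1 + CV²) for CVs of 36%, 19% and 53%. A version built on AUCinf (geometric mean 70.67, CV 29%) and half-life (CV 20%) gave similar results.

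**Range of LLOQ (assumed).** In the earlier study, "At 10 h after drug administration, the cytisine plasma levels exceeded LOQ in all subjects". The smallest Clast in Table 1 is 0.88 ng/mL, so that assay's LOQ lay below 0.88. This is an upper bound for an earlier assay, not this trial's LLOQ.

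**Share BLQ in the 1.5 mg group (within-subject CV 15-30%):**

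| LLOQ, ng/mL | Day 21 | Day 25 |
|---|---|---|
| 0.1 | 0% | 0.2-0.3% |
| 0.25 | 0.2-0.4% | 6-7% |
| 0.5 | 3-5% | 28-29% |
| 0.75 | 12-13% | 50-52% |

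At 0.5 this is about 0.28 × 18 = 5 of 18 subjects on Day 25.

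**Bias in the Day 25/Day 21 ratio when BLQ values are dropped (1.5 mg, half-life about 4.0 h, within-subject CV 20-30%):**

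| LLOQ, ng/mL | Planned model (fixed day, random subject) | Raw geometric means |
|---|---|---|
| 0.1 | about 0% | 0-1% |
| 0.25 | +2-3% | +8% |
| 0.5 | +6-11% | +27-29% |
| 0.88 | +14-22% | +52-53% |

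The model is less affected because a subject who loses Day 25 still contributes the earlier days, and the subject effect carries the information that this person runs low.

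**Sensitivity.** At a half-life of 4.8 h the model bias is +0.2 to +0.6% at LLOQ 0.25, +2 to +5% at 0.5 and +7 to +13% at 0.88. In the 3.0 mg group (within-subject CV 15-30%) the model ratio is about 0.48 up to LLOQ 0.25, 0.49-0.50 at 0.5 and 0.50-0.51 at 0.75.

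**At the planned sample size.** With 18 subjects at 1.5 mg and within-subject CV 20%, the estimate exceeded the full-data value in 60%, 97% and 97% of simulated trials at LLOQ 0.25, 0.5 and 0.75. With six subjects the average shift was similar (0.513 against 0.482 at LLOQ 0.5). At 0.75, 6 of 400 runs had a day with no quantifiable trough.

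**Scale.** Within-subject noise alone (CV 20%, log SD 0.198) gives a 90% CI half-width of 1.67 × 0.198 × √(2/18) = 0.110 on the log scale, about 11-12%. Differences between subjects in half-life would widen it.

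**Alternatives.** A left-censored likelihood gave 0.479 against full-data values of 0.476-0.478 at LLOQ 0.25 to 0.75. Substituting LLOQ/2 gave 0.45-0.51 over LLOQ 0.25 to 1.0.

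**The case against.** The strongest reply has four parts.

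1. **The size depends on a figure nobody outside the trial has seen.** This stands. At an LLOQ of 0.1 ng/mL or below there is almost nothing to lose. A reader might infer that the ratio is biased as a matter of fact; the documents do not support that.
2. **The planned model absorbs much of the loss.** This also stands. A reader might carry +27% or +52% over to the planned contrast, but those figures belong to raw geometric means. They still matter, because SAP 11.4.3 plans those means too, and the descriptive table and the ANOVA table could then disagree.
3. **The SAP nowhere says that BLQ troughs are dropped.** Correct: dropping is what software does with the log of zero, not a stated rule. Any loss would also be partly visible, since the summaries show N, n, minimum and median and individual concentrations are listed. The general clause in SAP 10.1 permits another method but names none, so the gap remains.
4. **Little hangs on this contrast.** The sample-size sections plan no hypothesis tests and call the objectives exploratory. SAP 10.6 puts the main interest in the dose-group comparison, which uses Day 25 Cmax and AUC and is untouched. Mainly one of four consecutive-day Cmin contrasts is affected, and troughs would still be seen to fall by about half over most of the LLOQ range. This limits the importance of the point but does not remove the defect.

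**Conclusion.** The defect holds in a conditional form. The stated BLQ rule cannot be carried through the log-scale analyses that the SAP specifies for Cmin, and no other section resolves it. If Day 25 troughs fall below the LLOQ and are dropped, the Day 25/Day 21 ratio would be biased upward, mainly in the 1.5 mg group.

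For a true ratio near 0.48, the planned contrast would read about 0.49 at an LLOQ of 0.25 ng/mL, 0.51-0.53 at 0.5 and 0.55-0.59 at 0.88 (0.48 times the biases above). At 0.5 the shift is a sizeable part of the interval's half-width. At 0.1 it vanishes.

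These figures rest on one-compartment superposition, 09:00 first doses, dose proportionality, no age effect on clearance, an assumed within-subject CV of 20-30% and assumed LLOQs. The documents support neither a definite bias nor one fixed size. The point warrants a SAP correction and does not put the dose-group comparison in doubt.

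**What to change.** Add to SAP 11.4.3.1: BLQ Cmin values are treated as left-censored at the LLOQ in the log-scale model with fixed study day and random subject, and in the Cmin geometric means. The number of BLQ values is reported by day and dose group. Where a small age subgroup does not support the censored fit, report the BLQ count and the median instead of a ratio.

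Use LLOQ/2 only as a sensitivity analysis. It is not reliably unbiased: its error ran from 0% to about −5% at a half-life of 4.02 h and up to about −7% at 4.8 h, similar in size to the bias it would replace at moderate LLOQs. Keep zero for arithmetic summaries and linear plots.

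The cost is a few sentences in the SAP and slightly more programming, with no change to data collection. The rule should be fixed before the first of the two database locks.

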11.4.3.1 Statistical Analysis of PK Parameters

Dosing Schedule Comparison

The dosing schedule comparison analysis will be performed separately within each of the dose groups.

In order to perform comparisons between schedule changes within each dose group, following logarithmic transformation, C_{max} values (post-last dose on days 3, 12, 16, 20, 24 and 25), and C_{min} values (pre-first dose on days 4, 13, 17, 21 and 25) will be subjected to an analysis of variance (ANOVA) including a fixed effect for study day and a random effect of subject. Point estimates and 90% confidence intervals (CI) will be constructed for the contrasts between consecutive study days using the residual mean square error obtained from the ANOVA. The point and interval estimates will be back-transformed to give estimates of the ratios of the geometric least squares means (LSmean) and corresponding 90% CI. In addition, estimated geometric means will be presented. The analysis will be performed by age group (18-65 yrs, >65 yrs, all ages).

Dose Group Comparison

The dose group comparison will be a between-group analysis.

Following logarithmic transformation, C_{max} , AUC_{0-t} and AUC_{0-inf} values on Day 25 will be subjected to an analysis of variance (ANOVA) including a fixed effect for dose group. Point estimates and 90% confidence intervals (CI) will be constructed for the contrast between the 1.5 mg and 3.0 mg dose groups using the residual mean square error obtained from the ANOVA. The point and interval estimates will be back-transformed to give estimates of the ratios of the geometric least squares means (LSmean) and corresponding 90% CI. In addition, estimated geometric means will be presented. The analysis will be performed by age group (18-65 yrs, >65 yrs, all ages).

11.5 PD ANALYSES

11.5.1 Number of Cigarettes Smoked and Expired CO

The number of cigarettes smoked in the past 24 hours will be recorded at Screening and daily from Day -1 to Post-Study. Expired air carbon monoxide (CO) data will be obtained at Screening and prior to discharge on days 4, 13, 17, 21 and 26.

The number of cigarettes smoked during the past 24 hours will be taken from the values recorded in the CRF (at CPU) for Screening and Day -1 to Day 3 and from the subject diaries thereafter. In order to evaluate any reduction in smoking, the number of cigarettes smoked daily will be assessed as well as smoking cessation status at Day 26. For each individual subject a smoking cessation status of 'Ceased smoking' will be defined as not having smoked any cigarettes for the past 24 hours on Day 26 and confirmed by an expired CO level <10ppm on Day 26. If these criteria are not satisfied, a smoking cessation status of 'Continued smoking' will be assigned to a subject, including subjects who have missing data at Day 26 for either the number of cigarettes smoked or expired CO level, or both.

The number of cigarettes smoked daily and smoking cessation status will be listed. Frequencies (n, %) of smoking cessation status at Day 26 will be calculated by dose group and age group. For those subjects who had ceased smoking by Day 26, frequencies of the day of first smoking cessation (defined as smoking 0 cigarettes and where cessation is sustained without relapse) will be presented by dose group and age group. Descriptive statistics (N, n, mean, SD, minimum, median and maximum) of absolute and change from baseline (Day -1) number of cigarettes smoked will be tabulated by dose group and age group. The mean absolute values and mean change from baseline will also be presented graphically. Individual subject plots of the number of cigarettes smoked daily will also be produced.

Expired CO levels will be included in the listing that presents the smoking cessation status data. Descriptive statistics (N, n, mean, SD, minimum, median and maximum) of absolute and change from baseline (Screening) expired CO results will be tabulated by dose group and age group. The mean absolute values and mean change from baseline values will also be presented graphically. Individual subject plots of expired CO levels will also be produced.

The summary tables described above for number of cigarettes smoked daily and expired CO levels will also be produced for two subgroups of subjects, defined by smoking cessation status ('Ceased smoking', 'Continued smoking'). The graphs described above of mean absolute values and mean change from baseline will also be presented by smoking cessation subgroup.

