**Figure 4: Dose Timing and Total Daily Dose**

Days	Regimen	Total Daily Dose		Approximate Interval
		1.5 mg Dose	3.0 mg Dose	
1-3	6 times daily	9.0 mg	18.0 mg	2 hours
4-12	5 times daily	7.5 mg	15.0 mg	2.5 hours
13-16	4 times daily	6.0 mg	12.0 mg	3 hours
17-20	3 times daily	4.5 mg	9.0 mg	4-5 hours
21-24	2 times daily	3.0 mg	6.0 mg	6 hours
25	Once daily	1.5 mg	3.0 mg	-

A total of 9 overnight stays in the clinic will be required over the 26-day study period. Subject entry into the study may be staggered in groups in order to facilitate study management activities but all subjects passing screening are to provide clinic visits as follows:

- Day -1 and Days 1-3 (4 overnight stays in clinic): Arrive at study clinic in the afternoon of Day -1, repeat select screening testing and verification of inclusion/exclusion criteria. Provide risks of smoking and quit advice according to WHO guidelines that evening. All subjects will fast for minimum of 10 hours prior to first dose on Day 1. Randomisation to treatment Group assignment will occur on the morning of Day 1, just prior to starting treatment. On the morning of Day 1, obtain baseline blood and urine and CO level, initiate Holter monitoring, receive study drug packets, begin treatment and provide required blood and urine samples. Subjects may have breakfast after first dose and continue with a standard meal schedule. On Days 1-3, various safety assessments and blood sample collections will occur. On the morning of Day 4 complete vital signs, ECG, blood for haematology and biochemistry testing, urine for cotinine test, expired CO, completion of tobacco craving questionnaire, safety assessment and collection of the pre-dose PK blood draw. Subject will then take first Day 4 dose followed by risks of smoking and quit advice, review of diary requirements, reminder of next clinic visit date and will be discharged.
- Day 4-11: Subjects to maintain dosing as per schedule.

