## **7.2. Smoking, Diet and Fluid Restrictions**

### **7.2.1. Smoking**

There will be minimal restrictions to smoking during days of confinement, such as all smoking must occur within designated area(s) only and subjects cannot smoke during active PK sampling period (i.e. subjects must have their last cigarette a minimum of 2 hours before dosing and can only start smoking after final PK sample). Subjects will go for a cigarette as a group and will need to have their last cigarette before 23:00 while they stay in the clinic. Clinic staff will review these guidelines with subjects during confinement and will monitor compliance.

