### **8.8. Selection and Timing of Dose for Each Subject**

First dose will be administered at approximately 9.00 a.m. on Day 1. Additional doses will be as per the Dosing Schedule (see [Figure 4](#)). A target time will be provided for each dose in the diary and actual time of dose will be recorded. For Days where dosing is every 2 to 3 hours, dosing should be  $\pm$  10 min within the targeted time. For Days where dosing is every 4-6 hours, dosing should be  $\pm$  30 min within the targeted time.

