14.5 Pharmacodynamics

14.5.1 Pharmacodynamic Data

Table 14.5.1.1	Summary of Absolute and Change from Baseline Daily Cigarette Consumption	PD Set
Table 14.5.1.2	Summary of Smoking Cessation Status	PD Set
Table 14.5.1.3	Summary of Absolute and Change from Baseline Daily Cigarette Consumption by Smoking Cessation Status	PD Set
Table 14.5.1.4	Summary of First Day of Smoking Cessation for Subjects Who Ceased Smoking by Day 26	PD Set
Table 14.5.1.5	Summary of Absolute and Change from Baseline Expired Air Carbon Monoxide (CO) Data	PD Set
Table 14.5.1.6	Summary of Absolute and Change from Baseline Expired Air Carbon Monoxide (CO) by Smoking Cessation Status	PD Set
Table 14.5.1.7	Summary of Absolute and Change from Baseline Urine Cotinine Data	PD Set
Table 14.5.1.8	Summary of Absolute and Change from Baseline Tobacco Craving Questionnaire – Short Form Scores	PD Set
Figure 14.5.1.1	Mean Daily Cigarette Consumption	PD Set
Figure 14.5.1.2	Mean Change from Baseline Daily Cigarette Consumption	PD Set
Figure 14.5.1.3	Mean Daily Cigarette Consumption by Smoking Cessation Status	PD Set

Figure 14.5.1.4	Mean Change from Baseline Daily Cigarette Consumption by PD Set Smoking Cessation Status	
Figure 14.5.1.5	Mean Expired Air Carbon Monoxide (CO) Data	PD Set
Figure 14.5.1.6	Mean Change from Baseline Expired Air Carbon Monoxide (CO) Data	PD Set
Figure 14.5.1.7	Mean Expired Air Carbon Monoxide (CO) by Smoking PD Set Cessation Status	
Figure 14.5.1.8	Mean Change from Baseline Expired Air Carbon Monoxide (CO) by Smoking Cessation Status	
Figure 14.5.1.9	Mean Urine Cotinine Data	PD Set
Figure 14.5.1.10	Mean Change from Baseline Urine Cotinine Data	PD Set
Figure 14.5.1.11	Mean Tobacco Craving Questionnaire – Short Form Total Score	PD Set
Figure 14.5.1.12	Mean Change from Baseline Tobacco Craving Questionnaire – Short Form Total Score	PD Set

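### Time since the last cigarette is neither standardised nor recorded at the on-treatment CO tests and can differ by visit, so mean CO can move between visits without any change in smoking

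*SAP*

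**What the plan says.** Reduction in expired CO from baseline, during treatment and at Day 26, is listed among the primary variables in SAP 4.1. On timing, SAP 11.5.1 has: "Expired air carbon monoxide (CO) data will be obtained at Screening and prior to discharge on days 4, 13, 17, 21 and 26". The same section tabulates and plots mean CO and mean change from Screening, overall and by smoking-cessation status. SAP 14.5.1 lists a figure titled "Mean Change from Baseline Expired Air Carbon Monoxide (CO) Data".

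Smoking in clinic is governed by Protocol 7.2.1: "subjects must have their last cigarette a minimum of 2 hours before dosing and can only start smoking after final PK sample". Subjects also "will need to have their last cigarette before 23:00 while they stay in the clinic". The section sets no time at which smoking may resume in the morning.

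The Screening CO has an explicit condition, no cigarette for 1 h before the test (Protocol 6.1.1, criterion 3). The on-treatment tests have none; the visit descriptions in Protocol 11.2 place them only before discharge. The diary (Protocol 13.9) collects daily cigarette counts and dose times, not the time of the last cigarette.

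**The concern.** Expired CO depends on how recently a person smoked as well as on how much. The 1 h condition at Screening shows that the protocol recognises this. After Screening, the interval is a by-product of the PK session the evening before, and that session changes as dosing steps down: the number and spacing of doses move the last dose, and sampling after it runs 5 h on Day 3 but 4 h on Days 12, 16 and 20.

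The planned CO figures will be read as a time course of drug effect across the taper. If the smoke-free interval differs by visit, part of any rise or fall reflects clinic timing, and the data collected would not allow the two to be separated. The drop from Screening is exposed in the same way, because a reading about 1 h after a cigarette is compared with readings that may follow many smoke-free hours.

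**Working it through.** The plan gives no figure for the smoke-free interval, so there is nothing to reproduce. It has to be derived.

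**Inputs from the documents**
- First dose: "First dose will be administered at approximately 9.00 a.m. on Day 1" (Protocol 8.8). No clock time is given for later days.
- Doses and approximate spacing (Protocol Figure 4): Days 1-3, 6 doses at 2 h; Days 4-12, 5 at 2.5 h; Days 13-16, 4 at 3 h; Days 17-20, 3 at 4-5 h.
- Last evening sample (Protocol Table 7; SAP 11.4.1): 5 h after the last dose on Day 3; 4 h on Days 12, 16 and 20. The Day 25 profile ends with a 24 h draw on Day 26.
- Smoking stops 2 h before the dose, resumes after the final PK sample, and ends by 23:00 (Protocol 7.2.1).

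**Assumptions**
- First dose at 09:00 every day, and CO read at about 09:00.
- For Days 4 to 21, the last evening draw counts as the final PK sample.
- No cigarette on the morning of the test.

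**Interval.** Last dose = 09:00 + (doses − 1) × spacing. If the last evening sample falls before 23:00, the last permitted cigarette is at 23:00; otherwise it is 2 h before the last dose.

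| CO day | Last dose, evening before | Sampling ends | Last permitted cigarette | Hours to 09:00 |
|---|---|---|---|---|
| 4 | 19:00 | 24:00 | 17:00 | 16 |
| 13 | 19:00 | 23:00 | 17:00 | 16 |
| 17 | 18:00 | 22:00 | 23:00 | 10 |
| 21, 4 h spacing | 17:00 | 21:00 | 23:00 | 10 |
| 21, 5 h spacing | 19:00 | 23:00 | 17:00 | 16 |

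For Day 26, if smoking is barred until the 24 h draw, the last cigarette is at 07:00 on Day 25, giving 24 + 2 = 26 h. If smoking is allowed between the 12 h sample (21:00) and 23:00, the interval is 10 h.

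**Sensitivity (Days 4 / 13 / 17)**
- First dose 08:00: 16 / 9 / 9 h.
- First dose 10:00: 16 / 16 / 17 h.
- First dose 09:00, with the next-morning pre-dose draw as the final PK sample: 16 / 16 / 17 h.
- First dose 09:00, with a cigarette allowed up to 07:00: only 2 h guaranteed on each day.

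At 09:00, Day 12 sampling ends exactly at the cut-off. The ±10 min dosing tolerance in Protocol 8.8 is then enough to decide whether a subject may smoke again that evening.

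**Effect on CO.** Assume first-order decay with half-life h of 3 to 6 h, and one cigarette per hour from 07:00 to 23:00 whenever permitted. CO at 09:00 (hour 33 counted from the previous midnight) is proportional to Σ 2^(−(33 − t)/h) over cigarette times t. For Day 13 the previous day's cigarettes run hourly from 07:00 to 17:00. For Day 17 they run from 07:00 to 16:00, plus any smoked between 22:00 and 23:00. Earlier days add a small carry-over.

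For h = 6:
- Day 13: 1.04 + 0.14 carry-over = 1.18.
- Day 17, no late cigarette: 0.88 + 0.14 = 1.03 (rounded from unrounded terms); ratio 0.87.
- Day 17, cigarettes at 22:00 and about 23:00: 1.03 + 0.28 + 0.31 = 1.62; ratio 1.37.

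| Late cigarettes on Day 16 | Day 17 / Day 13 ratio, h = 3 | h = 6 |
|---|---|---|
| none | 0.78 | 0.87 |
| one (22:00 or about 23:00) | 1.48-1.66 | 1.10-1.13 |
| two | 2.36 | 1.37 |

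The range is about 0.8 to 2.4 with smoking habit unchanged.

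For the comparison with Screening, the share of CO left after t hours is 2^(−t/h): 79-89% at 1 h, 10-31% at 10 h, 2.5-16% at 16 h and 0.2-5% at 26 h.

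**The case against.** The strongest objection is that no set of intervals can be read off the documents. The 09:00 time belongs to Day 1, the spacing is labelled approximate, and a one-hour shift in the first dose removes the Day 13 to Day 17 step. Treating the next-morning draw as the final sample removes most of it. Smoking after sampling is permitted, not required, so 10 h on Day 17 is a minimum. Check-in on Day 12 is just before the last dose, so part of the 2 h pre-dose abstinence may fall outside clinic supervision. All of this stands, and it rules out stating 16, 16 and 10 h as facts. It does not make the readings comparable: at 08:00 the step moves to between Days 4 and 13, and nothing collected would show which case applied to a given subject.

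A reader might infer that Day 17 CO must be two to four times Day 13 CO, from 2^(6/h) with h of 6 or 3. That assumes equal CO at 17:00 on Day 12 and 23:00 on Day 16. On the same schedule the Day 16 subject has not smoked from 16:00 to 22:00, so that calculation overstates the ratio, and without a late cigarette the direction reverses.

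It is also fair that the study is exploratory with no planned hypothesis test (Protocol 15.4), that the comparison of main interest is between dose groups (SAP 10.6), and that daily cigarette counts, cotinine and craving scores sit beside CO. These limit the harm. They do not make the CO time course interpretable on its own.

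**Conclusion.** The point holds as one about comparability across visits. Time since last cigarette is fixed only at Screening. Afterwards it can differ by visit under the protocol's own rules, and it is not recorded. Mean CO and change from baseline can therefore move with no change in smoking.

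The 16, 16, 10, 10-or-16 and up-to-26 h figures illustrate one reading. The Day 17 to Day 13 ratio of about 0.8 to 2.4 rests on that reading, an assumed half-life of 3 to 6 h and an assumed constant smoker. Neither its size nor its direction is fixed by the documents.

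A reader might further infer that the dose comparison is biased, or that the figure is bound to show early benefit followed by relapse. The documents support neither. Both groups follow the same timing, so the direction of the within-visit contrast is not affected, although very low CO values could compress a difference. A false relapse would also have to disagree with the daily cigarette counts. The amendment is worth making because it is cheap and CO reduction is a primary PD variable.

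**What to change.** 1. In Protocol 7.2.1, state which draw is the final PK sample on each clinic stay and whether smoking is allowed on the morning before the CO test.
2. Record the time of the last cigarette at every CO test.
3. In SAP 11.5.1, tabulate hours since last cigarette beside CO. Base CO interpretation on dose-group contrasts within a visit. Limit across-visit statements to visits whose recorded intervals match, without presuming that Days 4 and 13 do.
4. Optionally, add a CO test at check-in on Days 12, 16, 20 and 24. Protocol 7.2.1 already requires at least 2 h without smoking at that point, so the 1 h Screening condition would not describe it. These readings should be additional: they offer no Day 4 equivalent, and the Day 26 CO is needed for the cessation definition.

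For subjects already studied (SAP 9.3 describes an earlier lock for the non-elderly), the recorded dose and draw times allow the permitted smoking windows to be derived, though not actual smoking.

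The cost is one CRF field, short wording changes, an optional breath test, and weaker claims about the CO time trend.
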